4.0 Clinical Protocol

4.1 Study Design and Scope

The Optisure lead study is a multi-center, post-approval study that will be performed in compliance with the Conditions for Approval, as agreed upon with the FDA. Patients will be permitted to enroll in the study up to 30 days post-implant of the Optisure lead. Following a successful implant, patients will be followed every 6 months until 60 months (5 years). After patients complete 60 months of follow-up, their participation in the study will end. Patients who are consented prior to implant and for whom an implant is unsuccessful will be followed for 30 days for any adverse events and then withdrawn from the study, or may have an implant reattempted if the physician and patient choose to do so.

Patients who meet inclusion/exclusion criteria, sign an IRB/MEC approved informed consent, and have an implanted Optisure RV lead or attempted implant of the Optisure RV lead will be considered to be enrolled in the study. A total of 1725 patients will be enrolled at a maximum of 60 centers. Enrollment is expected to be completed between 20 and 24 months depending on the rate of enrollment.

Enrollment will be proportional to actual sales, and enrollment duration will not exceed 24 months. If implantation at the study sites is higher than the projected estimates (see section 4.5), then the study enrollment period will be decreased proportionately. Reporting will occur per section 6.0 of the protocol. In order to accomplish this, the study will be conducted at a maximum of 60 study centers.

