4.3 Sub-Study Design and Scope

This sub-study will determine the incidence of externalized conductors and other visual lead anomalies (as evidenced by imaging) and the risk of progression to electrical dysfunction in patients implanted with an Optisure HV lead. A minimum of 200 subjects who consent to participate in this sub-study will undergo cinefluoroscopy (AP, LAO 45° or the best possible LAO view, RAO 45° or the best possible RAO view) at the 24, 36, 48 and 60 month follow-up visits.

Expected Attrition in patients with high voltage leads

Withdrawals due to death

[figure not shown]
Assuming an annual mortality of 7% in the ICD patient population, the mortality at 5 years is 30% $[1 - (1-0.07)^5]$ In the recent RHYTHM ICD/QuickSite 1056K left heart lead study using CRT-D devices, the annual mortality was 12.8%, which would result in a mortality of 49% $[1 - (1-0.128)^5]$ at 5 years. If the ICD:CRT-D device mix is 60%:40% then the expected overall mortality in this study at 5 years is 38% ($=0.6 \times 0.30 + 0.4 \times 0.49$).

Withdrawals due to reasons other than death

In an ongoing St. Jude Medical post-approval study consisting of CRT devices and LV leads, 102 patients have been withdrawn for reasons other than death during an average of 22 months of follow-up. This translates to an attrition of 22% over 5 years.

Assuming that deaths and withdrawals are independent events, the total attrition is expected to be approximately 52% ($= 1 - (1 - 0.38) \times (1 - 0.22)$) over 5 years. With an expected attrition at 5 years to be 52%, a total of 417 subjects who consent to participate in this sub-study will be enrolled in order to have at least 200 subjects with fluoroscopy data available at the 60 month follow-up visit.

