5.0 Study Outcome Measures

5.1 Primary Outcome Measure

5.1.1 Freedom from RV Lead Related Complications

The primary outcome measure for the Optisure Lead Post Approval study is the complication free survival rate at 5 years for complications related to the Optisure RV leads.

The hypothesis is as follows:

H0: Complication free survival at 5 years \leq 92.5%

H1: Complication free survival at 5 years $>$ 92.5%

The desired outcome is to reject the null hypothesis. The null hypothesis will be rejected at the 5% significance level if the 95% Lower Confidence Bound (LCB) for the freedom from complications is greater than 92.5%.

Sample Size

Assuming that the time to first complication follows an exponential distribution and the complication-free survival at 5 years is 95%, a sample size of 645 patients provides 80% power to reject the null hypothesis of 92.5% complication-free survival years at the 5% significance level (See Appendix D for detailed sample size calculations).

Patient Group

All patients who had an attempted implant of the Optisure RV lead will be included in the analysis of this endpoint.

Analysis

All complications will be classified as related to the Optisure RV lead or unrelated.

The following complications will be included in this analysis:

- Cardiac perforation
- Lead dislodgement that occurred greater than 30 days after implant
- Lead insulation damage
- Lead fracture
- Abnormal RV lead performance (abnormal lead defibrillation impedance, abnormal lead pacing impedance, elevated pacing thresholds, loss of capture, failure to deliver therapy, loss of sensing, oversensing, undersensing)

- Other unexpected complications that are considered related to the RV lead

The survival time for all patients will be calculated as the number of days from implant or attempted implant to the date the complication was first discovered. For patients who do not experience a complication related to the Optisure RV lead at the time of their withdrawal, the survival time will be censored on the date of their withdrawal. For patients who have not experienced any complication related to the Optisure RV lead at the time of analysis, the survival time will be censored on the date of analysis. The endpoint will be evaluated using the Kaplan-Meier method and the 95% lower confidence bound (LCB) will be obtained by transformation from its log scale, based on Peto et al¹. The null hypothesis will be rejected if the 95% LCB is greater than 92.5%.

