5.3.5 Time from externalized conductors to electrical dysfunction

Lead Population

All Optisure leads with externalized conductors but without electrical dysfunction.

Analysis:

Time to electrical dysfunction will be analyzed using the Kaplan-Meier method. The zero time will be the date at which externalized conductor was detected. Those patients who experience an externalized conductor after enrollment, but do not experience an electrical dysfunction will be censored 3 years after enrollment in this trial.

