5.3.8 Time from externalized conductors to clinical intervention

Lead Population

All Optisure leads with externalized conductors.

Analysis:

Time to clinical intervention will be analyzed using the Kaplan-Meier method. The zero time will be the date at which externalized conductor was detected. Those patients who experience externalized conductor after enrollment but do not experience clinical intervention will be censored 3 years after enrollment in this trial.

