***Notes**

1. If the patient is in atrial fibrillation or atrial flutter, RA electrical measurements are not required.
2. If the patient is pacemaker dependent, RV sensing amplitude is not required.
3. As referenced under the Definitions in section 4.2, abnormal pacing lead impedances are defined as measured pacing impedances with values $\leq 200 \Omega$ or $\geq 2000 \Omega$. RV lead pacing impedances have been observed in typical clinical settings to be in the range of 200-1200 Ω for the majority of patients. However, lead pacing impedances measured up to 1999 Ω are considered to be within the normal bounds of the performance of the RV lead because characteristics such as non-

viable myocardium, lead-to-tissue contact, etc., specific to each patient have been known to produce measured pacing impedances that are higher than the observed 1200 Ω noted above.

Device diagnostics and archives of RV lead impedance values may also be used to diagnose potential lead failures. Alternatively, investigators should consult the respective device and lead user manuals, St. Jude Medical technical support or other St. Jude Medical clinical support personnel to diagnose potential lead failures.

The enrollment date for patients in the study will be the date when all protocol defined enrollment procedures (consent, implant and lead measurements) are completed.

Complete an Enrollment, Implant and Lead Measurements Case Report Forms and record all results. Complete an Adverse Event Case Report Form (if applicable) for all adverse events which occurred since the implant of the Optisure lead. Submit the forms to St. Jude Medical using the EDC system. Complete an Out of Service Form for any product used but not implanted (e.g. contaminated, dropped or opened in error).

Upload the device session record including all stored IEGMs to St. Jude Medical using the SJM EDC Portal device data upload utility. If the patient is enrolled after implant, provide the session record from the enrollment visit.

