9.4 Follow-Up Requirements

Lead measurements and adverse events (if applicable) will be obtained every 6 months from patients who have a successfully implanted Optisure lead until they reach the 5 year follow-up.

The schedule of follow-ups is based on the date of a successful Optisure lead implant. Table 4 outlines the time window that is permitted for each of the study interval visits.

Table 4: Study Interval Time Windows

Every 6 months thereafter until 5 years
± 90 days

The following electrical measurements* will be obtained at each follow up: capture thresholds for all implanted leads, signal amplitude measurements for the RV and RA leads, pacing lead impedance for all implanted leads and high voltage lead impedance for all implanted leads.

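### Four sub-study time-to-event analyses start at anomaly detection but censor event-free leads 3 years after enrollment, before or at three of the four scheduled imaging visits

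*Protocol*

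**What the plan says.** Four sub-study outcomes in the Protocol are Kaplan-Meier analyses from an imaging finding to a later event: 5.3.5 and 5.3.6 to electrical dysfunction, 5.3.8 and 5.3.9 to clinical intervention.

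- **Time zero.** Section 5.3.5: "The zero time will be the date at which externalized conductor was detected". The other three use the same origin for their own anomaly.
- **Censoring.** In 5.3.5 and 5.3.6, patients who "do not experience an electrical dysfunction will be censored 3 years after enrollment in this trial". In 5.3.8 and 5.3.9, those who "do not experience clinical intervention will be censored 3 years after enrollment in this trial".
- **Imaging.** Section 4.3 schedules cinefluoroscopy "at the 24, 36, 48 and 60 month follow-up visits". Section 9.4 repeats this.
- **Follow-up.** Section 4.1 follows patients six-monthly to 60 months and allows enrollment up to 30 days after implant.
- **Calendar.** Section 9.4: "The schedule of follow-ups is based on the date of a successful Optisure lead implant", with a window of ±90 days. The 3-year limit runs from enrollment, which section 9.2.1 dates separately: "The enrollment date for patients in the study will be the date when all protocol defined enrollment procedures" are complete.
- **Contrast.** For the primary endpoint (5.1.1), a patient who leaves without a complication is handled thus: "the survival time will be censored on the date of their withdrawal". Those still event-free are censored at the date of analysis.

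**The concern.** The censoring date is tied to enrollment and the clock to detection, and the two do not fit the imaging schedule. An event-free lead first found abnormal at month 48 or 60 would be censored before its own time zero, and no Kaplan-Meier routine can use a negative duration. No section describes a 3-year sub-study or gives a reason for 3 years.

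The sentence also has two readings. Taken literally it cuts only patients without the event. A lead that fails in month 50 keeps its event time, while a comparable lead that is still working leaves at month 36 or never enters. Alternatively it is meant as an administrative cut for everyone, and later failures are ignored too. The text does not say which.

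Section 4.3 names the risk of progression to electrical dysfunction as a purpose of the sub-study, and 4.5 sends sub-study results to FDA in the progress reports. The first reading biases that risk upward. The second discards most of the follow-up that the sub-study is built to collect.

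**Working it through.** **The plan's own figure.** Section 4.3 enrolls 417 so that 200 have 60-month images at 52% attrition: 200 / (1 - 0.52) = 416.7, rounded up to 417. It reproduces, and it shows that the design deliberately reaches month 60.

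**Dates only, no assumptions.** Event-free time = 36 months from enrollment minus the detection date. With enrollment 0 to 30 days after implant and visits ±90 days, the range is (1,095 - visit day - 90) to (1,095 - visit day + 30 + 90).

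| Detected at | Nominal | Range in days | Nominal maximum if followed to month 60 |
|---|---|---|---|
| 24 months | +12 months | +275 to +485 | +36 months |
| 36 months | 0 | -90 to +120 | +24 months |
| 48 months | -12 months | -455 to -245 | +12 months |
| 60 months | -24 months | -820 to -610 | 0 |

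The result is always negative at months 48 and 60.

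**Follow-up kept (illustration).** Assumptions not in the Protocol: anomaly hazard h = 1% per year (range 0.5 to 2%), detection only at scheduled visits, and constant attrition reaching the Protocol's 52% at 5 years, so a = -ln(0.48)/5 = 0.1468 per year.

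- Detections at visit v = 417 × [exp(-h × previous visit) - exp(-h × v)] × exp(-a × v), with 0 as the previous visit for the first. For v = 2, 3, 4, 5 years this gives 6.16, 2.62, 2.24 and 1.91, or 12.9 in all.
- Available person-years per detection = (1 - exp(-a × (5 - v)))/a = 2.427, 1.733, 0.930 and 0. Multiplied by detections: 14.94 + 4.54 + 2.08 + 0 = 21.56.
- Kept up to year 3: only 24-month detections contribute, (1 - exp(-a))/a = 0.930 each, and 6.16 × 0.930 = 5.73.
- Share kept: 5.73 / 21.56 = 27% (26 to 27% over the hazard range).
- Lost: 9.2 person-years from 24-month, 4.5 from 36-month and 2.1 from 48-month detections.
- Detections at 36 and 48 months are (2.62 + 2.24) / 12.93 = 38% of the total and lose essentially all usable event-free time to the rule. The 15% found at month 60 have none under any rule.

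**Effect on the estimate.** Large-sample simulation with the same detection mix and attrition, and an assumed progression hazard of 5, 10 or 20% per year:

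| 1-year progression | 5% | 10% | 20% |
|---|---|---|---|
| True, 1 - exp(-hazard) | 4.9% | 9.5% | 18.1% |
| Literal rule (only event-free leads cut) | 8.3% | 15.4% | 27.0% |
| Administrative cut for all | 5.0% | 9.5% | 18.1% |
| Censored at last follow-up | 4.9% | 9.5% | 18.0% |
| Share of events after year 3 | 72% | 71% | 69% |

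In the literal row, non-positive event-free times are removed. Setting them to zero gives the same estimate, because those leads are then never at risk when an event occurs.

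**Scale.** Expected progression events in 417 leads at h = 1% are about 1.0, 1.9 and 3.4. With correct censoring, the 1-year estimate would still have a standard deviation of about 7, 10 and 13 percentage points.

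**The case against.** The case for giving this little weight is reasonable. These outcomes are descriptive and untested. The primary endpoint, the 1725 and 417 sample sizes and the annual hazard rates in 5.3.1 to 5.3.3 do not use the rule. With one to three expected events, a bias of 3.4, 5.9 or 8.9 points is smaller than the sampling error. The bias also depends on the assumed mix: with equal detections at 24, 36 and 48 months and no attrition, a true 4.9% reads as 13.0%. Negative durations would be noticed at analysis. Imaging at a system revision more than 3 months after implant (9.3), and images from routine care (9.4), can find anomalies before month 24, where the rule leaves more time. The lead populations in these sections are also worded as all Optisure leads with the finding, not only the 417.

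Most of this stands as a limit on size. The percentages are illustrations, and a limit of 12 months on what can be estimated holds only at nominal scheduled dates. None of it repairs the rule for scheduled detections at months 36, 48 and 60. Noticing the problem at analysis would mean choosing the repair with the few events in view. Reading the text as 3 years after detection is not what it says, and for any scheduled detection after month 24 that limit falls beyond month 60.

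**Conclusion.** The concern holds. The Protocol fixes a censoring rule that conflicts with its own imaging schedule and length of follow-up. This is a stated rule that cannot be carried out as written, not a detail left to a statistical analysis plan. The negative times at months 48 and 60 follow from Protocol dates alone. The upward bias on the literal reading needs only that late events are kept while event-free leads are cut. The sizes (27% of person-years kept, 8.3% against 4.9% and so on) rest on assumed anomaly and progression hazards, scheduled detection only and the Protocol's 52% attrition. Earlier unscheduled detections would raise the share kept. It should be fixed, but it does not threaten the main study: data are collected to month 60 in any case, so corrected text recovers everything.

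**What to change.** In 5.3.5, 5.3.6, 5.3.8 and 5.3.9, replace the 3-year limit with censoring at the last date on which the lead's status is known: withdrawal, death, or the last visit up to 60 months. In 5.3.5 and 5.3.6, add the date a lead is taken out of service without adjudicated electrical dysfunction. This extends the withdrawal censoring already used in 5.1.1.

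If a 3-year cut is really intended, the text should say that it applies to events as well and runs from detection. Such a cut would bind only for anomalies found before month 24, so the first option is simpler.

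The cost is one sentence in each of four sections, with no new visits, data or sample size.

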5.3.6 Time from other visual lead anomalies by each subcategory to electrical dysfunction

Lead Population

All Optisure leads with other visual lead anomalies (by each subcategory) but without electrical dysfunction.

Analysis:

Time to electrical dysfunction will be analyzed using the Kaplan-Meier method. The zero time will be the date at which other visual lead anomaly (by each subcategory) was detected. Those patients who experience other visual lead anomaly (by each subcategory) after enrollment, but do not experience an electrical dysfunction will be censored 3 years after enrollment in this trial.

5.3.7 Adverse Event rate through 30 days post-intervention for lead (e.g. extraction, abandonment, revision, other)

Lead Population

All Optisure leads that require an intervention/revision (e.g. extraction, abandonment, other).

Analysis

The 30-day adverse event rate will be calculated as the number of adverse events within 30 days associated with lead related interventions divided by total lead related interventions.

5.3.8 Time from externalized conductors to clinical intervention

Lead Population

All Optisure leads with externalized conductors.

Analysis:

Time to clinical intervention will be analyzed using the Kaplan-Meier method. The zero time will be the date at which externalized conductor was detected. Those patients who experience externalized conductor after enrollment but do not experience clinical intervention will be censored 3 years after enrollment in this trial.

5.3.9 Time from other visual lead anomalies by each subcategory to clinical intervention

Lead Population

All Optisure leads with other visual lead anomalies (by each sub category).

Analysis:

Time to clinical intervention will be analyzed using the Kaplan-Meier method. The zero time will be the date at which other visual lead anomaly (by each subcategory) was detected. Those patients who experience other visual lead anomaly (by each subcategory) after enrollment but do not experience clinical intervention will be censored 3 years after enrollment in this trial.

5.3.10 Comparison of patients with lead compromise as evidenced by imaging (includes externalized conductors and other visual lead anomalies) to those without lead compromise

Patient Population

All the patients implanted with Optisure leads.

Analysis

Demographic and clinical parameters will be compared between patients who experience lead compromise as evidenced by imaging and those who do not experience lead compromise. Specifically, the variables age, gender, body mass index, lead size, lead model, and implant factors such as venous access site, number of other leads in the vasculature, fixation location in the right ventricle, level of activity (based on functional NYHA class scale I, II, III, IV), level of therapy that patient received (no ATP/shock, ATP or shock) and slack (grades 0, 1, 2, 3, 4 based on the scale described by Ha et al., 2010⁸) in the lead will be used for the comparison. Continuous variables such as age or body mass index will be compared using Student's T-tests while categorical variables such as gender or lead models will be compared using Pearson's Chi-square statistic. Point estimates and p-values will be provided from these analyses.

5.3.11 Comparison of patients with electrical dysfunction to those without electrical dysfunction.

Patient Population

All the patients implanted with Optisure leads.

Analysis

Demographic and clinical parameters will be compared between patients who experience electrical dysfunction and those who do not experience electrical dysfunction. Specifically, the variables age, gender body mass index, lead size, lead model, and implant factors such as venous access site, number of other leads in the vasculature, fixation location in the right ventricle, level of activity (based on functional NYHA class scale I, II, III, IV), level of therapy that patient received (no ATP/shock, ATP or shock) and slack in the lead (grades 0, 1, 2, 3, 4 based on the scale described by Ha et al, 2010⁸) will be used for the comparison. Continuous variables such as age or body mass index will be compared using Student's T-tests while categorical variables such as gender or lead models will be compared using Pearson's Chi-square statistic. Point estimates and p-values will be provided from these analyses.

